3.3 SCREENING VISIT PROCEDURES

Subjects will undergo a 45 min Screening Visit to obtain and determine their enrollment eligibility. During this visit, participants will complete a basic physical assessment (height, weight, heart rate, blood pressure, expired carbon monoxide, urine drug test, and pregnancy test (if applicable), saliva collection, and questionnaires: the Severity of Dependence Scale, THC use history and a standard screening packet asking demographics, health history and other product use.

The CRC will determine initial eligibility via basic physical assessment, toxicology screen, and inclusion/exclusion criteria. In the event of a positive toxicology test (except marijuana), subject will be dismissed immediately without payment and the remainder of the screening visit measures will not be completed. Participants who fail the pregnancy test, blood pressure test, or BMI assessment will be paid and dismissed. Clinical Research Coordinator should follow the Tobacco Research Center Pregnancy Test SOP for communicating results with the participant. Participants who indicate an exclusionary medication that they

neglected to report during the initial REDCap survey, will be dismissed without

payment. In all cases of early dismissal, any collection of biosamples will be discarded.

Upon determination of preliminary eligibility, the participant's saliva sample will be delivered to the lab for analysis. Participants must have saliva cotinine levels ≥ 30 ng/mL to be considered eligible for enrollment. NicAlert tests will be used to verify cotinine in cases when saliva cotinine samples are not able to be run quickly.

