	~7 AM	
 Nurses will measure and record the room temperature. Subject arrives at about 7 AM Nurses will ask the participant when they last smoked, vaped and used marijuana Expired CO measured: If <5 ppm, then admit; if ≥ 5 ppm, then dismiss Urine pregnancy test and drug toxicology test (if applicable), positive result then dismiss (if female this can be the voided urine) If male, participant voids urine, the discards Subject's personal e-cigarette and other tobacco products are taken away at admission No product until 8:30 AM
	~7:30	
 Participant rests and eats a light breakfast, may drink decaffeinated coffee or tea Liquids (water) will be given in preparation for urine sample

US#1 (Urine sample)	~8:20	Pre-STANDARDIZED Cannabis Vaping (pre-SVC)
		
PAX device filled with 125 mg of grounded cannabis leaf containing about 12% THC by the study team and weighed using microbalance
 
NOTE: The order of the first condition will not be the same between subjects. The order here is shown for the first participant.

BS#1 (blood sample)		
 After resting (before IV catheter insertion), baseline urine sample will be collected IV placed (plastic catheter in vein of forearm) 
Baseline Questionnaire Packet # 1, after IV placement
 
 Weigh PAX device containing cannabis before vaping BLOOD sample #1 (Pre-EC1) collected before standardized session BLOOD sample, catecholamines Blood sample should be taken just before first standardized session; ~8:20 AM 
BASELINE Heart Rate, by pulse oximeter, baseline skin temperature, baseline core body temperature

SCV	~8:40-8:45	C STANDARDIZED SESSION (Standardized Cannabis Vaping) -One (1) 5 second puff every 45 seconds for a maximum of 3 puffs with each puff followed by a 10 second breath hold. 
 • PAX will be turned on and allowed to pre-heat at temperature setting #2, which heats at about 193 °C. • Subjects will be voice-prompted (taped or in-person by CRC) • Gas trap procedures will be conducted (See Section 3.5.2) • The PAX device will be collected for weighing.
2-min BS#2	~8:47	2-MIN Post-SCV; Blood Sample #2 
 • BLOOD sample #2 collected after the SCV session • Heart Rate

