5-min BS#3	~8:50	5-MIN POST-SCV; Blood Sample #3 and Questionnaire Packet #2 
 • BLOOD sample #3 (5-min after last puff) • BLOOD sample, catecholamines • 5-min HEART RATE, 5-min SKIN TEMPERATURE TEST, Core body temperature • Questionnaire packet between 5-min and 15-min blood sample. CRC will administer.
	~8:55	10-min HEART RATE 
 • Questionnaire packet #3
15-min BS#4	~9:00	15-MIN POST-SCV; Blood Sample #4 
 • BLOOD sample #4 (15-min after last puff) • 15-min HEART RATE, 15-min SKIN TEMPERATURE TEST, Core body temperature • Questionnaire packet #4
	~9:05	20-min HEART RATE 
 • Questionnaire packet #5
	~9:10	25-min HEART RATE 
 • Questionnaire packet #6
30-min BS#5	~9:15	30-MIN POST-SCV; Blood Sample #5 
 • BLOOD sample #5 (30-min after last puff) • 30-min HEART RATE, 30-min SKIN TEMPERATURE TEST, Core body temperature
45-min BS#6	~9:30	45-MIN POST-SCV; Blood Sample #6 
 • BLOOD sample #6 (45-min after last puff)
55-min	~9:40	
 • Questionnaire packet #7
	~9:45	60-MIN POST-SCV; Blood Sample #7

1-h BS#7		
 BLOOD sample #7 (1-h after last puff) 1-h HEART RATE, 1-h SKIN TEMPERATURE TEST, Core body temperature
85-min	~10:00	
 Questionnaire packet #8
90-min BS#8	~10:15	90-min POST-SCV; Blood Sample #8 
 BLOOD sample #8 (90-min after last puff) 90-min HEART RATE, 90-min SKIN TEMPERATURE TEST, Core body temperature
2-h BS#9	~10:45	120-MIN POST-SCV; Blood Sample #9 
 BLOOD sample #9 (120 min after last puff from THC1) 2-h HEART RATE, 2-h SKIN TEMPERATURE TEST, Core body temperature
3-h BS#10	~11:45	180-MIN POST-SCV; Blood Sample #10 
 BLOOD sample #10 (180 min after last puff) 3-h HEART RATE, 3-h SKIN TEMPERATURE TEST, Core body temperature Light lunch at noon
6-h BS#11	~14:45	360-MIN POST-SCV; Blood Sample #11 and Questionnaire Packet #4 
 BLOOD sample #11 (2 h after last puff) 6-h HEART RATE, 6-h SKIN TEMPERATURE TEST, Core body temperature Nurses will administer Questionnaire Packet #9
6-h US#2	~14:55	6-h URINE SAMPLE (6-h post SVC)

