3.4.6 Sample Assays

- Plasma: nicotine, cotinine, 3-Hydroxicotinine (3HC)
- Urine: total nicotine metabolites (nicotine equivalents), NNAL, catecholamines, mercapturic acid, biomarkers of acrolein and propylene oxide, and other volatile organic compounds (VOCs).

4. 5B PAPERWORK AND PREPARATION FOR OUTPATIENT STUDY

- **Admission Request Form**
 - Use the current template for this form
 - Participant, date of admission (night before)
 - Address/phone number/DOB/SSN
 - Sent via PHI secure email (This is done after confirmation of the hospital and participant that this is the correct date) (Re-submit with updated date as needed)
- **Coversheet**
 - Use the current template for this form
 - Participant name and study ID on top as a label.
 - Edit date of admission and date of drop-off
 - General info about the study prepped on a per patient basis during admission
- **Flow Sheet (one long continuous document)**
 - Template existing & Study Staff and 5B review this at study initiation
 - Update this with e-cig brands/liquid info
 - Explain on the flow sheet the hospital will put PHI on this, we copy without PHI and file
- **Outpatient Form**
 - Make copy to 5B and we have the original in our chart
- **MD Orders**

- Pre-signed
- Name on the top corner and name/date **IN PENCIL**
- **Admit PE**
 - Name **IN PENCIL** at the top
 - Fill out by [name]/[name] at the time of the visit
- **Adverse Event Form**
 - Initialed if none occurred
- **Setup**
 - Should be done within 3 days before the admission and given to 5B within a day of the admission if possible.
 - Documents should be given to 5B in the order above
 - Paper clipped and given to them
 - 5B will make/use labels
 - Questionnaire Packet, organized and clipped by day
 - Consent form (there will be 3 signed at screening). **The original for 5B will go in the set-up.**
- At completion, CRC will copy de-identified:
 - Flowsheet
 - MD Orders
 - Admit PE
 - Discharge Sheet
 - AE Form (we take the original)

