6 DATA COLLECTION AND MANAGEMENT

6.1 DATA COLLECTION FORMS

Data Collection Forms entered by participants include:

1. Screening packet, except Physiological Assessment Form
2. REDCap Questionnaire
3. Research Ward Outpatient Questionnaire Packets 1-10

Data Collection Forms entered by Research Staff:

1. Physiological Assessment Form of the Screening Packet
2. Outpatient Product Weight Record

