6.3 DATA ANALYSIS

The study is not hypothesis-driven but will provide valuable data to guide future research as well as provide needed data on THC delivery and effects from vaping. Variables of interest include amount of THC inhaled, amount exhaled, and amount retained; pharmacokinetic parameters for THC, 11-OH-THC, and nicotine, the psychoactive compounds; heart rate and blood pressure change; and subjective effects.

Delivered and Retained Doses: Delivered THC and nicotine doses are estimated as the change in e-cigarette weight \times concentration of THC or nicotine in e-liquid. The amount of THC or nicotine systemically retained is estimated as delivered dose minus amount in gas traps.

THC, 11-OH-THC, and Nicotine Pharmacokinetics: Pharmacokinetic parameters will be estimated from blood THC and 11-OH-THC and plasma nicotine concentrations using Phoenix WinNonlin 6.3 (Pharsight Corporation, Mountain View, CA). Time to max concentration (T_{max}), max concentration (C_{max}), and area under the blood/plasma concentration-time curves (AUC) will be estimated using a non-compartmental model and trapezoidal rule. C_{max} , and $AUC_{0 \rightarrow \infty}$ will be adjusted for baseline nicotine levels.

Averages and 95% confidence intervals will be computed by e-liquid type (THC only or

THC+nicotine). Although this study is not hypothesis-driven, we will use mixed model analysis of variance (ANOVA) to assess differences in these variables between e-liquids type. Models will include sex as a covariate.

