The data collected at the screening visit and study visits 1-3 is located on RedCap under the project titled V-PAX study participant survey Database. This project includes the following forms: demographic information, screening packet, SDS, THC Use history questionnaire, NDSS, PS-ECDI, E-WISDOM, E-FTND, CES-D, MNWS, M-CES, PANAS, DEQ-5, MCQ-SF, M-SCALE, VAS.

- Location: https://redcap.ucsf.edu/redcap_v9.1.13/index.php?pid=24277

1. Crossover Specimen Log

The Crossover Specimen Log is a file in a database used to track all of the specimens collected during participants' orientation visit and inpatient study days. This log contains the following information: specimen type, dates and times of specimen collection, date of lab sample transfers, and volume/pH of urine specimens.

- a. Location: t-Drive
- b. Folder: 7845 V-PAX
- c. Sub-folder 1: Databases
- d. Subfolder 2: Logs
- e. name: 7845-V-PAX specimen Log

2. Urine Catecholamine Summary

The plasma Catecholamine Summary contains the catecholamine data from participants 7845-002-7845-018, including: norepinephrine, epinephrine, and dopamine per volume.

- Location: t-Drive
- Location: t-Drive
- Folder: 7845 V-PAX
- Sub-folder 1: Databases
- Subfolder 2: Logs
- name: 7845-V-PAX specimen Log
- Information is downloaded from ARUP Labs via email from program manager

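### Section 6.3 lists blood pressure change for analysis, but no blood pressure reading is scheduled on any study day

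*Combined protocol and SAP*

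**What the plan says.** Section 6.3 (Data Analysis) ends its list of variables of interest with "heart rate and blood pressure change; and subjective effects". It later adds that "we will use mixed model analysis of variance (ANOVA) to assess differences in these variables between e-liquids type", with sex as a covariate.

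The measurements come from the timed table in section 3.4.1(c), which is written out for Study Day 1 and declared to apply equally to Days 2 and 3. Its pre-vaping row reads "BASELINE Heart Rate, by pulse oximeter, baseline skin temperature, baseline core body temperature". The first full set after vaping reads "5-min HEART RATE, 5-min SKIN TEMPERATURE TEST, Core body temperature", and the same trio recurs through to 6 hours.

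Blood pressure appears in two other places. Section 1.5.1 gives systolic and diastolic eligibility limits. Section 3.3 (Screening Visit Procedures) includes it in "a basic physical assessment (height, weight, heart rate, blood pressure, expired carbon monoxide" and the items that follow, and a participant who fails the test there is dismissed.

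**The concern.** The analysis section promises a variable that the schedule does not collect. Change in blood pressure after vaping needs a reading before vaping and at least one after it, on the same day and under the same condition. Neither is scheduled.

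The variable matters to the study's purpose. Aim 2 concerns sympathetic stimulation by THC, nicotine and the two together. Blood pressure change is one of only two cardiovascular responses named in section 6.3, and section 1.5.2 excludes users of sympatholytic drugs. A reading not taken at the visit cannot be recovered. If staff take readings informally, their times may differ between visits, which would weaken a within-subject comparison.

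**Working it through.** No sample-size or power calculation bears on this point, and the plan gives no figure to reproduce. The check is a row count of section 3.4.1(c), followed by a search for any other source of study-day blood pressure.

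**Row count, one study day**

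| Measure | Scheduled times | Count |
|---|---|---|
| Heart rate | baseline; 2, 5, 10, 15, 20, 25, 30, 60, 90 min; 2, 3, 6 h | 13 |
| Skin and core temperature | baseline; 5, 15, 30, 60, 90 min; 2, 3, 6 h | 9 |
| Blood pressure | none | 0 |

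**Whole study** (3 visits, 14 subjects, from sections 1.4.1 and 1.42)

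- Heart rate: 13 × 3 × 14 = 546 scheduled readings.
- Skin and core temperature: 9 × 3 × 14 = 378 scheduled sets.
- Blood pressure: 0 × 3 × 14 = 0.

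**Could blood pressure be implied by another row?** The baseline heart rate is taken by pulse oximeter, so a blood pressure value is not a by-product of it. Each later physiological row names its measures one by one and omits blood pressure. The discharge check at the end of the table does not mention it either.

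**Could the screening value serve as a baseline?** No. It comes from an earlier day and there is no post-vaping value to pair with it.

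**Could other documents hold readings?** Section 4 names a ward flow sheet, physician orders and an admission examination form, and section 6.2 names a database for outpatient measures. Their contents are not given. They may include blood pressure, but the protocol does not say so, and a single admission reading would still not give a change.

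**Does section 6.1 help?** It lists "Physiological Assessment Form of the Screening Packet" among staff-entered forms and names no study-day vital-signs form. This is weak evidence, because it also names no form for study-day heart rate or temperature, which are scheduled. The finding rests on section 3.4.1(c).

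**The case against.** The mismatch itself is hard to dispute. The case on the other side concerns its weight and the remedy.

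- **Exploratory study.** Section 6.3 says the study is not driven by hypotheses, the aims do not name blood pressure, and no power calculation depends on it. This stands, and it limits the seriousness. It does not make the variable obtainable.
- **Leftover wording.** Section 6.3 speaks of e-cigarette weight and e-liquid types, which do not fit three loose-leaf conditions. Blood pressure may likewise be carried over from another protocol. This is plausible but unconfirmed. If it is so, deleting the phrase is the right repair.
- **Scope of the ANOVA.** The reference to these variables follows a paragraph on pharmacokinetic parameters, so it might not reach blood pressure. The wider reading is the natural one, but it is a reading. On the narrow one, blood pressure change is still a named variable of interest with no scheduled source.
- **Timing.** Appendix A reports completed participants in the past tense. If the visits are over, no readings can be added. Documenting ward readings or deleting the variable would still be possible.
- **Number of readings.** A change score strictly needs one baseline and one later reading. Nine time points are a convenience, chosen because staff are already measuring then.

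**Conclusion.** The inconsistency is real and should be fixed. Followed as written, the protocol yields no blood pressure change for any subject in any condition: 0 scheduled readings, against 546 for heart rate and 378 sets of skin and core temperature.

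The damage is limited to one exploratory variable. Heart rate, blood catecholamines (before vaping and at 5 minutes), temperatures and questionnaires all remain scheduled and still serve Aim 2.

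The conclusion assumes that section 3.4.1(c) is the complete study-day schedule. It would soften to a documentation gap if the ward flow sheet already records blood pressure at fixed times before and after vaping.

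**What to change.** Choose one of three routes so that sections 3.4.1(c) and 6.3 agree.

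1. **Measure it.** Add a blood pressure reading at the 9 rows that already carry heart rate, skin temperature and core temperature: baseline, 5, 15, 30, 60 and 90 minutes, and 2, 3 and 6 hours. In section 6.3, define change as the post-vaping value minus the same-day baseline, separately for systolic and diastolic pressure.
2. **Document it.** If the ward flow sheet already captures blood pressure before and after vaping, write those times into section 3.4.1(c) and give the same definition in section 6.3.
3. **Drop it.** If it is not and will not be measured, delete blood pressure change from section 6.3.

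Route 1 costs 9 cuff readings per visit, 9 × 3 = 27 per subject and 27 × 14 = 378 in all, at times when staff are already with the participant. The downside is brief cuff inflation during serial sampling. Using the arm without the catheter, after each blood draw, limits interference with the samples. The skin temperature site is not stated, so that reading should also come before the cuff is inflated. Routes 2 and 3 cost only a text edit and remain open if the visits are finished.

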1.4 STUDY DESIGN

1.4.1 Design Summary

The study is designed as a within-subjects single-blinded crossover study. Fourteen smokers of tobacco cigarettes and cannabis will switch between three conditions, namely: (a) vaping cannabis leaf, (b) vaping tobacco containing nicotine and (c) vaping a combination of cannabis leaf and tobacco containing nicotine. All participants will vape each product with the PAX loose-leaf vaporizer.

PAX vaporizers will be purchased by the study team. The cannabis leaf will be obtained through the National Institute on Drug Abuse Drug Supply Program. The tobacco containing nicotine, used in conditions (b) and (c) will come from commercially available Marlboro brand cigarettes. The same amount of cannabis or tobacco will be used in all conditions.

The study will be conducted during three outpatient visits separated by at least 48 hours. The order of treatment (cannabis leaf, tobacco with nicotine, cannabis leaf & tobacco with nicotine) will be counterbalanced between subjects. Subjects will be blinded to the content of the vaporizer on the study day but will be told during screening that they will vape cannabis alone, tobacco alone, and cannabis plus tobacco with nicotine.

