3.4 PHARMACOKINETIC STUDY: Outpatient Visits

3.4.2 Protocol for Outpatient Study

3.4.1(a) Marijuana preparation

Cannabis leaf material (11.7% THC) obtained from NIDA will be stored frozen in a locked room in the Zuckerberg San Francisco General Hospital Pharmacy. When a participant is randomized, the pharmacy will dispense of 250 mg of cannabis (this includes a back-up supply of 125 mg). All cannabis will then be stored in the freezer compartment of the medication refrigerator in the medication room of the Clinical Research Services Ward 5B.

Cannabis material to be used by a study participant will be humidified 24-36 hours before use. Using a petri dish placed at the bottom of the desiccator, 2 centrifuge tubes, each filled with sodium chloride solution, will be emptied into the dish. Cannabis cigarettes will be placed on the desiccator platform and maintained at room temperature overnight, which is expected to raise the moisture of the cannabis cigarettes by 3 to 5%. Cannabis material will be used within one hour after removal from the humidifier.

3.4.1(b) Hospital Admission Protocol

Before arrival to the hospital, the study co-I or CRC will meet the participant to collect a urine sample for drug testing. Only when it is confirmed that the participant is negative for all drugs other than cannabis, will we admit him/her on the research ward.

Upon arrival at the research ward, the following procedures will occur:

1. Nurses will ask the participant when they last smoked, vaped, or used THC.
 - If the participant smoked cigarettes or vaped e-cigarettes after 10pm the night before either admission, they will be dismissed from the study.
2. An expired CO test will be administered. If their CO reading is greater than or equal to 5 ppm, they will either be dismissed from the study or procedures will be delayed depending on PI discretion.
3. A pregnancy test will be administered to female participants. If the pregnancy test is positive, they will be dismissed from the study.
4. If the participant is female, the pregnancy test will also serve as the voided urine. If the participant is male, they will provide urine sample for discard.

3.4.1 (c) Outpatient Study Protocol

Samples	Time	Activity
STUDY DAY 1 (same procedures as Study Days 2 & 3)		

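### Heart-rate change is compared without the day's pre-vaping value as a covariate, although that value is collected; adding it is an optional, low-cost gain in precision whose size the documents do not fix

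*Combined protocol and SAP*

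**What the plan says.** Section 1.4.1 describes a "within-subjects single-blinded crossover study" with three conditions and 14 participants. Section 6.3 names "heart rate and blood pressure change; and subjective effects" among its variables of interest and then states that "we will use mixed model analysis of variance (ANOVA) to assess differences in these variables between e-liquids type". The only covariate named is in the sentence "Models will include sex as a covariate". The one baseline adjustment mentioned concerns nicotine: Cmax and AUC "will be adjusted for baseline nicotine levels". Section 6.3 does not define the reference point for change; the same day's pre-vaping reading is the natural one and is assumed here.

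The outpatient table in 3.4.1(c) has a pre-vaping row, at about 8:20, with "BASELINE Heart Rate, by pulse oximeter, baseline skin temperature, baseline core body temperature". The table's heading row applies it to all three study days. After vaping, heart rate is listed at 12 times: 2, 5, 10, 15, 20, 25 and 30 minutes, and 1, 1.5, 2, 3 and 6 hours. The table lists no blood pressure reading. Blood pressure appears in the eligibility criteria (1.5.1) and in the screening procedures (3.3).

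**The concern.** In a parallel-group trial, a change score removes stable differences between people. In a crossover with a participant effect in the model, those differences are already gone. What the day's baseline can still offer is information about how that person differs from his or her own average on that day. Subtracting it assumes that such a deviation carries over one for one to the post-vaping reading. If it carries over less, the subtraction adds noise. The schedule gives one baseline heart-rate entry per day, so the same error enters all 12 changes of that day, and averaging over post-vaping times does not reduce it.

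The 95% intervals are the main product of a descriptive study of this size, and heart rate is the most densely sampled sympathetic measure under Aim 2. Intervals wider than the data require would be an avoidable loss.

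**Working it through.** **Inputs.** From the documents: 14 participants (1.42), three visits each, so 14 × 3 = 42 participant-days; three cyclic sequences as laid out in 1.6.2, used 5, 5 and 4 times; one baseline heart rate per day. The documents give no SD, correlation, effect size or power figure, so there is no stated figure to reproduce. Assumed: sb and sp, the within-person day-to-day SDs of baseline and post-vaping heart rate; and r, the within-person, same-day correlation of the two. This r is not repeatability from one day to the next, and a high correlation between people does not count towards it.

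**Formulae.** With participant effects in the model, the variance of a condition contrast is proportional to

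- change score: sp² + sb² − 2·r·sb·sp
- baseline as covariate: sp²(1 − r²)

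The difference is (sb − r·sp)², which is never negative. It is zero when r·sp/sb = 1, that is, when the within-person slope is 1.

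**Equal SDs.** The variances are 2(1 − r) and 1 − r², so the ratio of standard errors (covariate to change) is √((1 + r)/2). At r=0.5 this is √0.75 = 0.866.

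**Post-vaping SD 1.5 times baseline SD.** The variances are 3.25 − 3r and 2.25(1 − r²). At r=0.2 they are 2.65 and 2.16, a standard error ratio of √(2.16/2.65) = 0.903. At r=0.7 they are 1.15 and 1.1475, a ratio of 0.999. The slope equals 1 at r = 1/1.5 = 0.67, which is why the gain disappears around there.

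**Finite-sample check.** The formulae ignore the lost degree of freedom and chance imbalance in baseline. A simulation on the 1.6.2 layout (4,000 runs per setting; participant, period and condition effects) counts both. Residual degrees of freedom are 42 − 14 − 2 − 2 = 24 for change and 23 with the covariate. Period was included in the simulation although 6.3 does not name it. Ratios below 1 favour the covariate.

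| r | Equal SDs: SE ratio, formula | Equal SDs: 95% CI width ratio, simulated | Post SD 1.5×: SE ratio, formula | Post SD 1.5×: 95% CI width ratio, simulated |
|---|---|---|---|---|
| 0.2 | 0.775 | 0.794 | 0.903 | 0.920 |
| 0.5 | 0.866 | 0.885 | 0.982 | 1.005 |
| 0.7 | 0.922 | 0.944 | 0.999 | 1.022 |
| 0.8 | 0.949 | 0.970 | 0.976 | 0.998 |
| 0.9 | 0.975 | 0.997 | 0.882 | 0.901 |

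The largest loss in any setting run was 1.022, about 2%.

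**Change can still be reported.** Subtracting the baseline from the outcome while keeping it as a covariate only shifts the baseline coefficient by 1. In a numerical check, both forms gave the same contrast (0.3617) and the same standard error (0.2878).

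**The case against.** The strongest reply is that the gain may be small or absent. The baseline at about 8:20 and the first post-vaping reading at about 8:47 are 27 minutes apart on the same morning, so r could be high there. It may be lower at 6 hours, and no single r covers readings from 2 to 360 minutes. If post-vaping heart rate is more variable than baseline, the gain shrinks further over much of the range; if baseline is the more variable, it grows. The documents settle none of this. That objection stands: only a range that reaches zero gain can be defended.

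A second reply is that 6.3 calls the study not hypothesis-driven, so precision hardly matters. This carries less weight, because the same section makes averages with 95% intervals the output.

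A reader might also draw stronger conclusions that the documents do not support:

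- That Aim 2 rests on heart rate alone. Section 1.3 also names subjective effects, and the schedule collects catecholamines and skin and core temperature.
- That every questionnaire should be adjusted in the same way. The contents of baseline Packet #1 are not given, and forms that rate the product or the drug effect, such as the mCEQ and DEQ-5, may have no meaningful pre-vaping score.
- That blood pressure is never taken on study days. The ward flow sheet and admission examination listed in section 4 are not reproduced, so only the mismatch with the study-day table is shown.

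**Conclusion.** The point holds as an optional precision improvement. Section 6.3 names heart rate change as an outcome and names no covariate that can reduce within-person error, although a suitable one is measured on each study day. Apart from a small finite-sample cost, covariate adjustment is never less precise than the change score. How much better it is rests on assumed values of r and the SDs. In the settings shown, the effect on the 95% interval runs from about 21% shorter to about 2% wider.

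It would be tempting to infer a fixed saving, or its equivalent in extra participants, or to call the planned analysis wrong. Neither follows. The saving depends on quantities that are not in the documents, and change scores give unbiased contrasts, so no conclusion is invalidated.

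The blood pressure mismatch does not depend on r. It is a separate point that needs reconciling.

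**What to change.** In 6.3, define change as measured from the same day's pre-vaping reading. Model post-vaping heart rate (or its change) with condition as a fixed effect, participant as a random effect, and two covariates: that day's pre-vaping value and the participant's mean pre-vaping value over the study days. The second keeps the within-person slope from being mixed with the between-person slope. Do the same for skin and core temperature, which have a recorded baseline, and for questionnaire scales only where a meaningful pre-vaping score exists. Whether period and time also enter the model is a separate question that this argument does not settle.

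The cost is a few lines of text and 1 to 2 degrees of freedom, with no new measurements, visits or participants.

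Separately, reconcile the blood pressure entry: either state where and when it is recorded on study days, or amend the variable list in 6.3.

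### Section 6.3 applies an e-liquid dose formula to plant material, so the weight-based THC dose can differ between cannabis and cannabis plus tobacco when true delivery does not

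*Combined protocol and SAP*

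**What the plan says.** Section 6.3 (Data Analysis) lists the amounts of THC inhaled, exhaled and retained among the variables of interest. "Delivered THC and nicotine doses are estimated as the change in e-cigarette weight" times the concentration of THC or nicotine in e-liquid. Then: "The amount of THC or nicotine systemically retained is estimated as delivered dose minus amount in gas traps". For reporting, "Averages and 95% confidence intervals will be computed by e-liquid type", with the types given as THC only and THC plus nicotine, and a mixed-model ANOVA assesses differences in these variables between types.

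The product is described elsewhere. Section 1.4.1: "All participants will vape each product with the PAX loose-leaf vaporizer". Section 3.4.1(a): "Cannabis leaf material (11.7% THC) obtained from NIDA" is humidified before use, "which is expected to raise the moisture of the cannabis cigarettes by 3 to 5" percent, and "Cannabis material will be used within one hour after removal from the humidifier". The study-day table in Section 3.4.1(c) has "PAX device filled with 125 mg of grounded cannabis leaf containing about 12% THC by the study team and weighed using microbalance". In that table the device is weighed in the block at about 8:20, pre-heated to about 193 °C within the session at about 8:40, puffed, and then collected for weighing. The text closing the table puts 125 mg of leaf and 125 mg of tobacco together in one device for C+T.

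**The concern.** For a uniform liquid, weight lost times concentration is a reasonable dose estimate. For a plant load it is right only if the fraction of THC released equals the fraction of load mass lost. Three documented features leave that without support:

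- Water is added to the cannabis shortly before use and can be driven off on heating. No humidification is described for the tobacco.
- Pre-heating lies between the weighings, so mass lost then counts as delivered.
- C+T gives one weight change for two materials, with no rule for splitting it, so mass lost by the tobacco changes the calculated THC dose.

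The documents describe no moisture correction, pre-heat blank, assay of spent material or calibration. Aim 3 plans to assess device emissions, but no method is given and no link to the dose is made.

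At stake are two named variables and the THC delivery part of Aim 1. The error can differ by condition, so the crossover does not cancel it, and a 95% confidence interval does not show it.

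**Working it through.** The plan gives no numeric dose to reproduce. The check is a mass balance.

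**Inputs from the documents:** leaf 11.7% THC; cannabis load 125 mg; C+T load 125 + 125 = 250 mg; added moisture 3 to 5%, read here as percent of load mass. **Assumed, because the documents give none:** mass losses and the exhaled fraction.

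**1. Concentration.** THC loaded = 125 × 0.117 = 14.625 mg. In C+T, 14.625 / 250 = 5.85%. For an assumed 10 mg loss in C+T, the rule gives 10 × 0.117 = 1.17 mg or 10 × 0.0585 = 0.585 mg, a factor of 2. The two leaf figures, 11.7% and about 12%, differ only by 12 / 11.7 = 1.026.

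**2. C versus C+T.** Let Lc and Lt be the fractional mass losses of cannabis and tobacco, with the cannabis behaving the same in both conditions, and k = Lt / Lc.

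- Rule in C: 125 × Lc × 0.117 = 14.625 Lc.
- Rule in C+T at 5.85%: 125 × (Lc + Lt) × 0.0585 = 7.3125 (Lc + Lt).
- Ratio C+T / C = 0.5 × (1 + k).

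The true ratio is 1. The rule returns:

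| Assumed k | Ratio at 5.85% |
|---|---|
| 0.5 | 0.75 |
| 0.75 | 0.88 |
| 1 | 1.00 |
| 1.5 | 1.25 |

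If 11.7% were used in C+T, the ratio would be 1 + k, which is right only if the tobacco lost no mass.

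**3. How moisture alone could move k.** Added water w = 125 × 0.03 = 3.75 mg to 125 × 0.05 = 6.25 mg. Suppose all of it is lost, the tobacco is not humidified, and each 125 mg of material loses a further m mg. Then k = m / (m + w):

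| Assumed m (mg) | k (w = 3.75; 6.25) | Ratio at 5.85% |
|---|---|---|
| 10 | 0.727; 0.615 | 0.86; 0.81 |
| 20 | 0.842; 0.762 | 0.92; 0.88 |
| 40 | 0.914; 0.865 | 0.96; 0.93 |

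**4. Direction within C.** If all the added water is lost, the rule counts 3.75 × 0.117 = 0.44 mg to 6.25 × 0.117 = 0.73 mg of it as THC. That is a gross amount. Water lost in proportion to its share of the load is consistent with the rule; only a disproportionate loss inflates the dose. Vapour richer in THC than the load works the other way. For an assumed 10 mg loss the rule gives 1.17 mg. With the added water gone and the remainder carrying 11.7% THC, the dose is (10 − 6.25) × 0.117 = 0.44 mg to (10 − 3.75) × 0.117 = 0.73 mg. With the remainder all THC, the ceiling is 3.75 to 6.25 mg.

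**5. Retained dose.** Retained = delivered − trap, so an error in delivered dose passes through in full. With an assumed 30% exhaled, a delivered dose wrong by a factor of 0.5 or 2 makes the retained amount wrong by (0.5 − 0.3) / 0.7 = 0.29 or (2 − 0.3) / 0.7 = 2.43.

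**6. Nicotine.** No tobacco nicotine concentration is given, and the sample assays in Section 3.4.6 include none of the tobacco. The source also conflicts: Marlboro in Section 1.4.1, American Spirit Blue in Section 3.4.1(c).

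**The case against.** The strongest reply is that the e-liquid wording is carry-over, that Section 6.3 calls the doses estimates, that the study is declared not hypothesis-driven, and that the sizes above rest on assumed losses. Much of this stands. The wording alone is editorial, and the THC rule can be computed once the loaded material is substituted. The 5.85% is derived, and it shifts slightly if 125 mg is the weight before humidification. The cannabis may also behave differently in a load twice as large. But calling a value an estimate does not state the equal-composition assumption, and the plan still puts these values into a between-condition model.

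A reader might infer that delivered dose is overstated because of the water. The documents do not support that: the 0.44 to 0.73 mg is not a net error, and THC-rich vapour would act in the opposite direction.

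A reader might also infer that both doses should be deleted. That goes too far. They are named variables, and exhaled amount and blood levels do not replace an inhaled dose. Exhaled amount alone cannot tell less inhaled from more retained.

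Nor do all mechanisms apply everywhere. For nicotine in the tobacco-only condition, only pre-heat loss and the general equal-composition assumption remain.

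**Conclusion.** The concern holds as a limit on two outcomes. Followed as written, the rule can produce a C versus C+T difference in THC dose that is not real, and it leaves open a 2-fold choice of concentration in C+T. The ratio 0.5 × (1 + k) assumes 5.85%, equal 125 mg portions and the same cannabis behaviour in both conditions. The value of k is unknown, so the range 0.75 to 1.25 is an illustration and not an estimate of the bias. Net direction and size cannot be fixed from the documents. The nicotine dose cannot be computed from them at all.

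Cmax, Tmax, AUC and trap amount do not use this rule, so the point does not reach them. It does not follow that they are sound; their validity is a separate question not examined here.

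**What to change.** In Section 6.3:

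1. Replace the e-cigarette and e-liquid wording with PAX weight change and the loaded material.
2. Keep delivered and retained dose only as nominal, approximate, descriptive values, and state the equal-composition assumption.
3. Name the concentration per load and analyte: THC in C; THC in C+T (5.85% if 11.7% is the leaf figure at loaded weight); nicotine in T and C+T, with its source. Say whether the leaf figure refers to stored or humidified weight.
4. Remove the weight-based doses from the mixed-model C versus C+T comparison. Base that comparison on measured THC and nicotine exposure (Cmax, AUC), with trap amount and PAX weight change in mg reported alongside.
5. If Aim 3 emission data or an assay of kept spent material exist, use them to calibrate the dose.
6. Reconcile the tobacco source between Sections 1.4.1 and 3.4.1(c), because the nicotine concentration depends on it.

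Items 1, 2 and 4 are text changes; the gas-trap filters and the THC and nicotine blood draws are already planned. Items 3 and 6 need the records of what was used, and for nicotine a documented content. Item 5 means extra laboratory work and may no longer be possible: Appendix A already refers to completed participants, and the documents do not say whether spent material was kept. The price is that inhaled and retained milligrams become approximate, and exposure measures do not fully replace them.
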